APPENDIX 7. LIST OF SENSITIVE CYTOCHROME P450 SUBSTRATES: CYP2C9, CYP2C19, CYP2D6, AND CYP3A4

Substrates can be classified by their sensitivity as:

- sensitive substrates (≥ 5 -fold increase in AUC with a strong inhibitor of the cytochrome P450 [CYP] specified)
- moderately sensitive substrates (≥ 2 to < 5 -fold increase in AUC with a strong inhibitor of the CYP specified)

Following is a table of sensitive substrates of CYP2C9, CYP2C19, CYP2D6, and CYP3A4.

Table 23: Sensitive Substrates of CYP2C9, CYP2C19, CYP2D6, and CYP3A4

	Sensitive substrates	Moderate sensitive substrates
CYP2C9	celecoxib(c)	glimepiride, phenytoin, tolbutamide, warfarin
CYP2C19	S-mephenytoin, omeprazole	diazepam, lansoprazole(d), rabeprazole, voriconazole
CYP2D6	atomoxetine, desipramine, dextromethorphan, eliglustat(e), nebivolol, nortriptyline, perphenazine, tolterodine, venlafaxine	amitriptyline, encainide, imipramine, metoprolol, propafenone, propranolol, tramadol, trimipramine,
CYP3A4	alfentanil, avanafil, buspirone, conivaptan, darifenacin, darunavir(f), ebastine, everolimus, ibrutinib, lomitapide, lovastatin(g), midazolam, naloxegol, nisoldipine, saquinavir(f), simvastatin(g), sirolimus, tacrolimus, tipranavir(f), triazolam, vardenafil	alprazolam, aprepitant, atorvastatin(c), colchicine, eliglustat(e), pimozide, rilpivirine, rivaroxaban, tadalafil
	budesonide, dasatinib, dronedarone, eletriptan, eplerenone, felodipine, indinavir(f), lurasidone, maraviroc, quetiapine, sildenafil, ticagrelor, tolvaptan	

Please note the following: Additional drug-drug interaction data can be obtained from the University of Washington Metabolism and Transport Drug Interaction Database [Hachad et al. (2010), Hum Genomics, 5(1):61-72].

APPENDIX 8. LIST OF DRUGS KNOWN TO PROLONG QT/QTc INTERVAL

The table below includes a list of drugs known to prolong QT/QTc interval from <http://medicine.iupui.edu/clinpharm/ddis/main-table/>

Note: Medicines on this list must be reviewed by Principal Investigators on an ongoing basis to assure updates.

LIST OF DRUGS KNOWN TO PROLONG QT/QTc INTERVAL	
Generic Name	Brand Names (Partial List)
Alfuzosin	Uroxatral [®]
Amantadine	Symmetrel [®] , Symadine [®]
Amiodarone	Cordarone [®] , Pacerone [®] , Nexterone [®]
Amisulpride (Only on Non-US Market)	Solian [®] , Supitac [®] , Soltus [®] , Amitrex [®] , Amazeo [®]
Amitriptyline	Elavil [®] (Discontinued 6/13), Tryptomer [®] , Tryptizol [®] , Laroxyl [®] , Saroten [®] , Sarotex [®] , Lentizol [®] , Endep [®]
Anagrelide	Agrylin [®] , Xagrid [®]
Apomorphine	Apokyn [®] , Ixense [®] , Spontane [®] , Uprima [®]
Aripiprazole	Abilify [®] , Aripiprex [®]
Arsenic trioxide	Trisenox [®]
Artemimol+piperazine	Eurartesim [®]
Asenapine	Saphris [®] , Sycrest [®]
Astemizole (Removed from Market)	Hismanal [®]
Atazanavir	Reyataz [®]
Atomoxetine	Strattera [®]
Azithromycin	Zithromax [®] , Zmax [®]
Bedaquiline	Sirturo [®]
Bepidil (Removed from Market)	Vascor [®]
Bortezomib	Velcade [®] , Bortecad [®]
Bosutinib	Bosulif [®]
Ceritinib	Zykadia [®]
Chloral hydrate	Aquachloral [®] , Novo-Chlorhydrate [®] , Somnos [®] , Noctec [®] , Somnote [®]
Chloroquine	Aralen [®]
Chlorpromazine	Thorazine [®] , Largactil [®] , Megaphen [®]
Cilostazol	Pletal [®]
Ciprofloxacin	Cipro [®] , Cipro-XR [®] , Neofloxin [®]
Cisapride (Removed from Market)	Propulsid [®]
Citalopram	Celexa [®] , Cipramil [®]
Clarithromycin	Biaxin [®] , Prevpac [®]
Clomipramine	Anafranil [®]
Clozapine	Clozaril [®] , Fazaclo [®] , Versacloz [®]
Cocaine	Cocaine
Crizotinib	Xalkori [®]

APPENDIX 8. LIST OF DRUGS KNOWN TO PROLONG QT/QTc INTERVAL (CONTINUED)

LIST OF DRUGS KNOWN TO PROLONG QT/QTc INTERVAL	
Generic Name	Brand Names (Partial List)
Cyamemazine (cyamepromazine) (Only on Non-US Market)	Tercian [®]
Dabrafenib	Tafinlar [®]
Dasatinib	Sprycel [®]
Degarelix	Firmagon [®]
Delamanid (Only on Non-US Market)	Deltyba [®]
Desipramine	Pertofranc [®] , Norpramine [®]
Dexmedetomidine	Precedex [®] , Dexdor [®] , Dexdomitor [®]
Diphenhydramine	Benadryl [®] , Nytol [®] , Unisom [®] , Sominex [®] , Dimedrol [®] , Daedalon [®]
Disopyramide	Norpace [®]
Dofetilide	Tikosyn [®]
Dolasetron	Anzemet [®]
Domperidone (Only on Non-US Market)	Motilium [®] , Motillium [®] , Motinorm Costi [®] , Nomit [®]
Donepezil	Aricept [®]
Doxepin	Sinequan [®] , Silenor [®] , Aponal [®] , Adapine [®] , Doxal [®] , Deptran [®] , Siquan [®]
Dronedarone	Multaq [®]
Droperidol	Inapsine [®] , Droleptan [®] , Dridol [®] , Xomolix [®]
Eribulin mesylate	Halaven [®]
Erythromycin	E.E.S. [®] , Robimycin [®] , EMycin [®] , Erymax [®] , Ery-Tab [®] , Eryc Ranbaxy [®] , Erypar [®] , Eryped [®] , Erythrocin Stearate Filmtab [®] , Erythrocot [®] , E-Base [®] , Erythroped [®] , Ilosone [®] , MY-E [®] , Pediamycin [®] , Zineryt [®] , Abbotycin [®] , Abbotycin-ES [®] , Erycin [®] , PCE Dispertab [®] , Stiemycine [®] , Acnasol [®] , Tiloryth [®]
Escitalopram	Ciprallex [®] , Lexapro [®] , Nexito [®] , Anxiset-E [®] (India), Exodus [®] (Brazil), Esto [®] (Israel), Seroplex [®] , Elicea [®] , Lexamil [®] , Lexam [®] , Entact [®] (Greece), Losita [®] (Bangladesh), Reposil [®] (Chile), Animaxen [®] (Colombia), Esitalo [®] (Australia), Lexamil [®] (South Africa)
Famotidine	Pepcid [®] , Fluxid [®] , Quamatel [®]
Felbamate	Felbatol [®]
Fingolimod	Gilenya [®]
Flecainide	Tambocor [®] , Almarytm [®] , Apocard [®] , Ecrinal [®] , Flécaine [®]
Fluconazole	Diflucan [®] , Trican [®]
Fluoxetine	Prozac [®] , Sarafem [®] , Fontex [®]
Foscarnet	Foscavir [®]
Furosemide (frusemide)	Lasix [®] , Fusid [®] , Frumex [®]
Galantamine	Reminyl [®] , Nivalin [®] , Razadyne-ER [®] ,
Gatifloxacin (Removed from Market)	Tequin [®]
Gemifloxacin	Factive [®]
Granisetron	Kytril [®] , Sancuso [®] , Granisol [®]

APPENDIX 8. LIST OF DRUGS KNOWN TO PROLONG QT/QTc INTERVAL (CONTINUED)

LIST OF DRUGS KNOWN TO PROLONG QT/QTc INTERVAL	
Generic Name	Brand Names (Partial List)
Grepafloxacin	Raxar [®]
Halofantrine	Halfan [®]
Haloperidol	Haldol [®] (US & UK), Aloperidin [®] , Bioperidolo [®] , Brotopon [®] , Dozic [®] , Duraperidol [®] (Germany), Einalon S [®] , Eukystol [®] , Halosten [®] , Keselan [®] , Linton [®] , Peluces [®] , Serenace [®] , Serenase [®] , Sigaperidol [®]
Hydrochlorothiazide	Apo-Hydro [®] , Aquazide H [®] , BP Zide [®] , Dichlotride [®] , Hydrodiuril [®] , HydroSaluric [®] , Hydrochlorot [®] , Microzide [®] , Esidrex [®] , Oretic [®]
Hydrocodone - ER	Hysingla [™] ER, Zohydro ER
Hydroxychloroquine	Plaquenil [®] , Quineprox [®]
Hydroxyzine	Atarax [®] , Vistaril [®] , Aterax [®] , Alamon [®] , Durrax [®] , Equipose [®] , Masmoran [®] , Orgatraz [®] , Paxistil [®] Quiness [®] , Tran-Q [®] , Tranquizine [®]
Ibutilide	Corvert [®]
Iloperidone	Fanapt [®] , Fanapta [®] , Zomaril [®]
Imipramine (mepipramine)	Tofranil [®]
Indapamide	Lozol [®] , Natrilix [®] , Insig [®]
Isradipine	Dynacirc [®]
Itraconazole	Sporanox [®] , Onmel [®]
Ivabradine	Procoralan [®] , Coralan [®] , Corlontor [®] , Coraxan [®] , Ivabid [®] , Bradia [®]
Ketoconazole	Nizoral [®] , Sebizole [®] , Ketomed [®] , Keton [®]
Lapatinib	Tykerb [®] , Tyverb [®]
Lenvatinib	Lenvima [®]
Leuprolide	Lupron [®] , Eligard [®] , Viadur [®] , Carcinil [®] , Enanton [®] , Leuplin [®] , Lucrin [®] , Procren [®] , Prostat [®] and others
Levofloxacin	Levaquin [®] , Tavanic [®]
Levomepromazine (Only on Non-US Market)	Nosinan [®] , Nozinan [®] , Levoprome [®]
Levomethadyl (Removed from Market)	Orlaam [®]
Lithium	Eskalith [®] , Lithobid [®]
Mesoridazine (Removed from Market)	Serentil [®]
Methadone	Dolophine [®] , Symoron [®] , Amidone [®] , Methadose [®] , Physeptone [®] , Heptadon [®]
Metoclopramide	Reglan [®] , Afipran [®] , Maxolon [®] , Cerucal [®] , Clopamon [®] , Clopra [®] , Maxeran [®] , Maxolon [®] , Metozolv [®] , Plasil [®] , Pramin [®] , Primperan [®] , Perinorm [®]
Metronidazole	Flagyl [®] and many others
Mifepristone	Korlym [®] , Mifeprex [®]
Mirabegron	Myrbetriq [®]
Mirtazapine	Remeron
Moexipril/HCTZ	Uniretic [®] , Univasc [®]
Moxifloxacin	Avelox [®] , Avalox [®] , Avelon [®]

APPENDIX 8. LIST OF DRUGS KNOWN TO PROLONG QT/QTc INTERVAL (CONTINUED)

LIST OF DRUGS KNOWN TO PROLONG QT/QTc INTERVAL	
Generic Name	Brand Names (Partial List)
Nelfinavir	Viracept [®]
Nicardipine	Cardene [®]
Nilotinib	Tasigna [®]
Norfloxacin	Noroxin [®] , Ambigram [®]
Nortriptyline	Pamelor [®] , Sensoval [®] , Aventyl [®] , Norpress [®] , Allegron [®] , Noritren [®] , Nortrilen [®]
Ofloxacin	Floxin [®]
Olanzapine	Zyprexa [®] , Zydys [®] , Relprevv [®]
Ondansetron	Zofran [®] , Anset [®] , Ondemet [®] , Zuplenz [®] , Emetron [®] , Ondavell [®] , Emeset [®] , Ondisolv [®] , Setronax [®]
Osimertinib	Tagrisso [®]
Oxaliplatin	Eloxatin [®]
Oxytocin	Pitocin [®] , Syntocinon [®]
Paliperidone	Invega [®] , Xepilon [®]
Panobinostat	Farydak [®]
Pantoprazole	Protonix [®] and others
Papaverine HCl	none
Paroxetine	Paxil [®] , Aropax [®] , Pexeva [®] , Seroxat [®] , Sereupin [®]
Pasireotide	Signifor [®]
Pazopanib	Votrient [®]
Pentamidine	Pentam [®]
Perflutren lipid microspheres	Definity [®]
Pimozide	Orap [®]
Pipamperone (Only on Non-US Market)	Dipiperon (E.U), Propitan (Japan)
Posaconazole	Noxafil [®] , Posamol [®]
Probucol (Removed from Market)	Lorelco [®]
Procainamide	Pronestyl [®] , Procan [®]
Promethazine	Phenergan [®]
Propofol	Diprivan [®] , Propoven [®]
Quetiapine	Seroquel [®]
Quinidine	Quinaglute [®] , Duraquin [®] , Quinact [®] , Quinidex [®] , Cin-Quin [®] , Quinora [®]
Quinine sulfate	Qalaquin [®]
Ranolazine	Ranexa [®] , Ranozex [®]
Rilpivirine	Edurant [®] , Complera [®] , Eviplera [®]
Risperidone	Risperdal [®]
Ritonavir	Norvir [®]
Roxithromycin (Only on Non-US Market)	Rulide [®] , Xthrocin [®] , Roxl-150 [®] , Roxo [®] , Surlid [®] , Rulide [®] , Biaxsig [®] , Roxar [®] , Roximycin [®] , Roxomycin [®] , Rulid [®] , Tirabycin [®] , Coroxin [®]

APPENDIX 8. LIST OF DRUGS KNOWN TO PROLONG QT/QTc INTERVAL (CONTINUED)

LIST OF DRUGS KNOWN TO PROLONG QT/QTc INTERVAL	
Generic Name	Brand Names (Partial List)
Saquinavir	Invirase [®] (combo)
Sertindole (Only on Non-US Market)	Serdolect [®] , Serlect [®]
Sertraline	Zoloft [®] , Lustral [®] , Daxid [®] , Altruline [®] , Besitran [®] , Deprax [®] , Elrval [®] , Emergen [®] , Gladem [®] , Implicane [®] , Sedoran [®] , Sealdin [®] , SerivoLowfin [®] , Stimuloton [®] , Tresleen [®] , Sertralin Bluefish [®]
Sevoflurane	Ulane [®] , Sojourn [®]
Solifenacin	VESIcare [®]
Sorafenib	Nexavar [®]
Sotalol	Betapace [®] , Sotalex [®] , Sotacor [®]
Sparfloxacin (Removed from Market)	Zagam [®]
Sulpiride (Only on Non-US Market)	Dogmatil [®] , Dolmatil [®] , Eglonyl [®] , Espiride [®] , Modal [®] , Sulpor [®]
Sunitinib	Sutent [®]
Tacrolimus	Prograf [®] , Prograf [®] , Advagraf [®] , Protopic [®]
Tamoxifen	Nolvadex [®] (discontinued 6/13), Istubal [®] , Valodex [®]
Telaprevir	Incivo [®]
Telavancin	Vibativ [®]
Telithromycin	Ketek [®]
Terfenadine (Removed from Market)	Seldane [®]
Tetrabenazine	Nitoman [®] , Xenazine [®]
Thioridazine	Mellaril [®] , Novoridazine [®] , Thioril [®]
Tizanidine	Zanaflex [®] , Sirdalud [®]
Tolterodine	Detrol [®] , Detrusitol [®]
Toremifene	Fareston [®]
Torsemide	Demadex [®] , Diuver [®] , Examide [®]
Trazodone	Desyrel [®] (discontinued 6/13), Oleptro [®] , Beneficat [®] , Deprax [®] , Desirel [®] , Molipaxin [®] , Thombran [®] , Trazorel [®] , Trialodine [®] , Trittico [®] , Mesyrel [®]
Trimipramine	Surmontil [®] , Rhotrimine [®] , Stangyl [®]
Tropisetron (Only on Non-US Market)	Navoban [®] , Setrovel [®]
Vandetanib	Caprelsa [®]
Vardenafil	Levitra [®]
Vemurafenib	Zelboraf [®]
Venlafaxine	Effexor [®] , Efexor [®]
Voriconazole	VFend [®]
Vorinostat	Zolinza [®]
Ziprasidone	Geodon [®] , Zeldox [®]

APPENDIX 9. MANAGEMENT OF TUMOR LYSIS SYNDROME

Prior studies with the CDK inhibitors, flavopiridol and dinaciclib have shown that these drugs can cause severe and potentially life-threatening TLS in patients with CLL. The Investigator must assess the risk of TLS for each patient based on the tumor type, extent of disease and patient factors such as comorbidities, in particular renal function, and age.

All subjects enrolled in this study, even those considered at low risk for TLS, must take prophylaxis.

Guidance for TLS risk assessment, prophylaxis, and monitoring, based on the recommendations for CLL/SLL patients in the [Venclexta \[US Prescribing Information\] Rev 2022](#), are provided in [Table 24](#). Patients with B-cell malignancies should be assessed for low, medium, or high risk for TLS, with prophylaxis and monitoring guidance as per [Table 24](#).

Patients with AML should be assessed for low, intermediate, or high risk of TLS, as defined in [Figure 3](#). Additional considerations, prophylaxis, and monitoring of TLS in AML patients are as follows:

- All AML subjects should have white blood cell count less than $25 \times 10^9/L$ prior to initiation of venetoclax; cytoreduction (e.g., with hydroxyurea) prior to venetoclax treatment may be required if white blood cell counts greater than $25 \times 10^9/L$ or lower than this cutoff but rapidly rising counts.
- Prior to first dose of venetoclax, provide all patients with prophylactic measures including adequate hydration and anti-hyperuricemic agents (see [Table 24](#)) and continue during ramp-up phase.
- Blood chemistry (potassium, uric acid, phosphorus, calcium, and creatinine) should be assessed prior to initiation of treatment with venetoclax, and pre-existing abnormalities corrected.
- Monitor blood chemistries for TLS at pre-dose, 6 to 8 hours after each new venetoclax dose during ramp-up, and 24 hours after reaching final ramp-up dose (i.e., pre-dose on Day 3 in Cohorts 12–25).
- For patients with risk factors for TLS (e.g., circulating blasts, high burden of leukemia involvement in bone marrow, elevated pretreatment lactate dehydrogenase [LDH] levels, or reduced renal function), consider additional measures, including increased laboratory monitoring.

[figure not shown]
Table 24: Guidelines for Prophylaxis and Monitoring for Patients with CLL/SLL and other B-cell Malignancies at Risk of TLS

RISK	Tumor/CLL Leukemic Burden	Prophylaxis		Hospital setting and biochemical monitoring
		Hydration	Anti- hyperuricemic therapy	
LOW	All LN <5cm AND ALC <25 × 10 ⁹ /L	Oral 1.5 – 2.0 L	Allopurinol starting ≥2 days before treatment	Outpatient 
 • TLS blood panel monitoring* 
 ○ pre-first dose; 6 to 8 hr, and 24 hr After reaching final ramp up dose: 
 ○ pre-dose only
MEDIUM	ANY LN 5 to <10 cm OR ALC ≥25 × 10 ⁹ /L	Oral 1.5 – 2.0 L and consider intravenous (150 to 200 mL/hr)	Allopurinol starting ≥2 days before treatment	Outpatient, but consider hospitalization based on age or renal function (creatinine clearance <80 ml/min) 
 • TLS blood panel monitoring* 
 ○ pre-first dose; 6 to 8 hr, and 24 hr ○ for subsequent ramp-up doses: pre-dose
HIGH	ANY LN ≥10 cm OR ALC ≥25 × 10 ⁹ /L AND any LN ≥10 cm	Oral 1.5 – 2.0 L and intravenous (150 to 200 ml/hr)	Allopurinol starting ≥2 days before treatment or consider rasburicase if baseline uric acid above ULN	Inpatient for 24 hours post first dose 
 • TLS blood panel monitoring* 
 ○ pre-first dose; 6 to 8 hr, and 24 hr Outpatient 
 ○ for subsequent ramp-up doses: pre-dose; 6 to 8 hr, and 24 hr

Abbreviations: ALC = absolute lymphocyte count; LN = lymph node; TLS = tumor lysis syndrome;
ULN = upper limit of normal.

*Sampling timepoints ±30 minute window permitted.

TLS blood chemistry panel must include potassium, uric acid, phosphorus, calcium, and creatinine.

Figure 3: TLS Risk Assessment for AML

TLS risk assessment for acute leukemia. Classification of acute myeloid leukemia depends on white blood cell (WBC) counts and relative lactate dehydrogenase (LDH) levels to upper limit of normal (ULN) (adapted from [Cairo 2010](#)).

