4.3.2.1. Administration Schedules and Doses of Voruciclib + Venetoclax

Amendment 11 – IS_{2w,2w} Dosing Schedule

For Cycle 1 in combination cohorts 12–19, the dosing will be as follows ([Table 5](#)):

- Venetoclax will be ramped up starting with 100 mg on Day 1, 200 mg on Days 2–21, then 400 mg administered as a single agent on Days 22–28.
- Voruciclib dosing will be administered on Days 3–14 at the appropriate Cohort Dose ([Table 3](#)).

For Cycle 2 and beyond, the dosing will be as follows:

- Venetoclax 200 mg will be administered on Days 1–21, and 400 mg administered as a single agent on Days 22–28.
- Voruciclib at the cohort dose ([Table 3](#)) on Days 1–14.

Venetoclax should be taken with a meal and water. When both venetoclax and voruciclib are to be taken, venetoclax should be taken first with a meal followed by voruciclib at least 2 hours later (e.g., meal completed at 8 a.m. with venetoclax, dose of voruciclib taken after 10:00 a.m.). Voruciclib tablets must not be chewed, crushed, or broken.

Table 5: Administration Schedules of Voruciclib given in Combination with Venetoclax (IS_{2w,2w})

Administration Schedule of Voruciclib IS _{2w,2w} and Venetoclax per 28-day Cycle					
Cycle 1	Day 1	Day 2	Days 3 to 14	Days 15 to 21	Days 22 to 28
Venetoclax	100 mg	200 mg	200 mg	200 mg	400 mg
Voruciclib QD	-	-	Cohort dose	None	None
Voruciclib QOD ^a	-	-	50 mg ^a	None	None
Cycle 2 and beyond	Days 1 to 14		Days 15 to 21		Days 22 to 28
Venetoclax	200 mg		200 mg		400 mg
Voruciclib QD	Cohort dose		None		None
Voruciclib QOD ^a	50 mg ^a		None		None

Abbreviation: QOD = once every other day

^a For cohort 12, the dose of voruciclib will be 50 mg once every other day (QOD) on Days 3, 5, 7, 9, 11, and 13 of Cycle 1, and on Days 1, 3, 5, 7, 9, 11, and 13 of Cycle 2 and beyond.

Amendment 12 – IS_{3w,1w} Dosing Schedule

For Cycle 1 in combination cohorts 21–25, the dosing will be as follows (Table 6):

- Venetoclax dose will be ramped up starting with 100 mg on Day 1, 200 mg on Days 2–21, then 400 mg administered as a single agent on Days 22–28.
- Voruciclib dosing will be administered on Days 3–21 at the appropriate Cohort Dose (Table 4).

For Cycle 2 and beyond, the dosing will be as follows:

- Venetoclax 200 mg will be administered on Days 1–21, and 400 mg administered as a single agent on Days 22–28.
- Voruciclib at the cohort dose (Table 4) will be administered on Days 1–21.

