4.9. Tumor Lysis Syndrome (TLS)

TLS includes electrolyte abnormalities (hyperkalemia, hypocalcemia, hyperuricemia, and hyperphosphatemia), cardiac dysrhythmias, and renal failure. TLS is a known risk in subjects treated with CDK9 inhibitors. The risk of TLS depends on tumor type, tumor burden, and subject factors such as pre-existing renal impairment and splenomegaly. Therefore, risk assessment for TLS, prophylaxis, and monitoring, including assessment of need for hospitalization, is required for all subjects. Investigators must institute appropriate prophylactic measures, including for low-risk subjects, during screening and prior to Cycle 1 Day 1.

Risk assessment for subjects with B-cell tumors and AML are provided in [Appendix 9](#) in [Table 24](#) and [Figure 3](#), respectively. All AML subjects should have white blood cell count less than $25 \times 10^9/L$ prior to initiation of venetoclax; cytoreduction prior to treatment may be required.

Recommended TLS prophylaxis and monitoring in [Table 24](#) are per those indicated for CLL/SLL patients in the [Venclexta \[US Prescribing Information\] Rev 2022](#). Additional guidance for subjects with AML is provided in [Appendix 9](#). Guidance on the diagnosis of TLS is provided in [Appendix 10](#).

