9.14.2. Voruciclib + Venetoclax Combination Therapy

Pre-dose specimens should be drawn within 2 hours prior to dosing and post-dose within +30 minutes of designated post-dose sampling times.

Blood samples for characterization of **voruciclib PK** will be collected in Cohorts 12–19 and 21–25 as shown in [Table 14](#) and [Table 15](#), relative to dosing of voruciclib.

Table 14: PK Sample Collection for Voruciclib, Cohort 12 (QOD Dosing)

Cycle	Day	Time of Collection	
		Pre-dose	Post-dose
1	3	X	2, 4, 6 hours
	4*	-	approximately 24 hours after Day 3 dose
	8	-	approximately 24 hours after Day 7 dose
	13	X	2, 4, 6 hours
	14	-	approximately 24 hours after Day 13 dose
	21	anytime during clinic visit	
2	1	X	-
4, 6	1, 14 (± 3 days)	anytime during clinic visit	
Every 3 cycles thereafter	1, 14 (± 3 days)	anytime during clinic visit	

* Day 4 sample to be collected only if the subject is able to visit the clinic.

Table 15: PK Sample Collection for Voruciclib, Cohorts 13–19 and 21–25 (QD Dosing)

Cycle	Day	Time of Collection	
		Pre-dose	Post-dose
1	3	X	2, 4, 6 hours
	4*	X (approximately 24 hours after Day 3 dose)	-
	8	X (approximately 24 hours after Day 7 dose)	-
	14	X	2, 4, 6 hours
	15	-	approximately 24 hours after Day 14 dose
	21	anytime during clinic visit	
2	1	X	-
4, 6	1, 14 (± 3 days)	anytime during clinic visit	
Every 3 cycles thereafter	1, 14 (± 3 days)	anytime during clinic visit	

* Day 4 sample to be collected only if the subject is able to visit the clinic.

Drug-Drug Interaction (DDI) Assessment: Voruciclib exposures (when co-administered with venetoclax) will be compared to historical single agent data to assess DDI and the effect of venetoclax on voruciclib PK.

Blood samples for characterization of **venetoclax PK** will be collected in Cohorts 12–19 and 21–25 as shown in [Table 16](#) and [Table 17](#), relative to dosing of venetoclax.

Table 16: PK Sample Collection for Venetoclax, Cohort 12 (QOD Dosing)

Cycle	Day	Time of Collection	
		Pre-dose	Post-dose
1	13	X	2, 4, 6, 8 hours
	14	X (approximately 24 hours after Day 13 dose)	-
	21	anytime during clinic visit	
2	1	X	2, 4, and 6-hours post-dose of venetoclax (voruciclib to be dosed 6 hours after venetoclax administration, after completion of the 6- hour sample collection)
4, 6	1, 14 (± 3 days)	anytime during clinic visit	
Every 3 cycles thereafter	1, 14 (± 3 days)	anytime during clinic visit	

Table 17: PK Sample Collection for Venetoclax, Cohorts 13–19 and 21–25 (QD Dosing)

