APPENDIX 3. SCHEDULE OF ASSESSMENTS - AML SUBJECTS ONLY – COMBINATION THERAPY

	Screening ^b	Cycle 1- Inclusive of Venetoclax Ramp-up ^c					Cycle 2		Cycle 3 and Subsequent Cycles ^d	End of Study ^e
	-28 to -1	1 ^a	2	3	8	14	1	14	1	30 days (± 3 days) Post Last Dose Study Drug
Informed consent	X									
Medical history/Prior Treatment/Demographics	X									
Physical examination	X	X								X
Symptom-directed exam ^f				X	X	X	X		X	
Vital signs ^g	X	X		X	X	X	X		X	X
Height	X									
Weight	X						X		X	X
ECOG performance status	X	X					X		X	X
Pregnancy test ^h	X	X					X		X	X
HIV testing ⁱ	X									
Hepatitis B and C testing ^j	X									
Adverse events ^k		X	X	X	X	X	X	X	X	X
Concomitant medication ^l	X	X	X	X	X	X	X	X	X	X
ECG ^m	X	X		X	X	X	X			X
CBC with differential ⁿ	X	X		X	X	X	X	X	X	X
Serum chemistry ^o	X	X	X	X	X	X	X	X	X	X
TLS risk assessment and monitoring ^o	X	X	X	X						
Coagulation ^p	X		X			X	X		X	X
Urinalysis (dipstick) ^q	X						X			X
Baseline chest x-ray ^r	X									
Issue and assess compliance diary ^s		X					X		X	
Dispense study drug(s) ^t		X					X		X	
Disease assessment, bone marrow aspirate ^u	X						X		X	X
Cytogenetics ^v	X									
Molecular mutations ^w	optional									
Blood for PD/biomarker assays ^x		X		X		X				
Blood for PK analysis	See specific PK collection timepoints in table below									

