APPENDIX 10. CAIRO-BISHOP CRITERIA FOR DIAGNOSIS OF TUMOR LYSIS SYNDROME

For a diagnosis of laboratory tumor lysis syndrome (TLS), 2 or more of the metabolic abnormalities shown in Table 25 must be present during the same 24-hour period within 3 days before the start of therapy, or up to 7 days after. Clinical TLS requires the presence of laboratory TLS plus an increased creatinine, seizures, cardiac dysrhythmia, or death.

Table 25: Definitions of Laboratory and Clinical Tumor Lysis Syndrome

Metabolic Abnormality	Criteria for Classification of Laboratory TLS	Criteria for Classification of Clinical TLS
Hyperuricemia	Uric acid >8.0 mg/dL (475.8 µmol/L) in adults or above the ULN for age in children	
Hyperphosphatemia	Adults: phosphorus >4.5 mg/dL (1.5 µmol/L) Children: phosphorus >6.5 mg/dL (2.1 µmol/L)	
Hyperkalemia	Potassium >6.0 mmol/L	Cardiac dysrhythmia or sudden death probably or definitely caused by hyperkalemia
Hypocalcemia	Corrected calcium <7.0 mg/dL (1.75 mmol/L) or ionized calcium <1.12 (0.3 mmol/L) ^a	Cardiac dysrhythmia, sudden death, seizure, neuromuscular irritability (tetany, paresthesias, muscle twitching, carpopedal spasm, Trousseau's sign, Chvostek's sign, laryngospasm, or bronchospasm), hypotension, or heart failure probably or definitely caused by hypocalcemia
Acute kidney injury ^b	Not applicable	Increase in serum creatinine level of 0.3 mg/dL (26.5 µmol/L) (or single value >1.5 times the ULN of the age-appropriate range if no baseline creatinine measure is available) or the presence of oliguria, defined as an average urine output of <0.5 ml/kg/hr for 6 hr

Abbreviations: hr = hour; TLS = tumor lysis syndrome; ULN = upper limit of normal.

^a The corrected calcium level in mg/dL = measured calcium level in mg/dL + 0.8 × (4 – albumin g/dL).

^b Acute kidney injury is defined as an increase in the creatinine level of at least 0.3 mg/dL (26.5 µmol/L) or a period of oliguria lasting 6 hr or more. By definition, if acute kidney injury is present, the patient has clinical TLS. See Levin et al for data about acute kidney injury.

Reference: [Howard 2011](#).

Signature Page for VV-CLIN-000078 v14.0

Approval	[name] Medical 30-Jan-2024 22:35:50 GMT+0000
----------	--

Approval	[name] Regulatory 31-Jan-2024 04:13:21 GMT+0000
----------	--

Signature Page for VV-CLIN-000078 v14.0

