Additionally, the number and percentage of subjects with TEAEs will also be summarized by PT for each dose cohort, tumor type, and in total. Drug-related TEAEs, treatment-emergent SAEs, drug-related treatment-emergent SAEs, TEAEs leading to discontinuation of study drug, drug-related TEAEs leading to discontinuation of study drug, TEAEs leading to dose reduction/interruption of study drug, and drug-related TEAEs leading to dose reduction/interruption of study drug will be summarized in the same manner. For these summaries, subjects with multiple adverse events will be counted only once per PT.

Summaries will be provided by the worst CTCAE grade and PT for the number and percentage of subjects with TEAEs and drug-related TEAEs. Subjects with multiple adverse events will be counted only once by the highest CTCAE grade within a PT.

Furthermore, Tumor Lysis Syndrome (TLS) is considered AEs of special interest. The frequency and percentage of laboratory and clinical TLS (determined by Modified Cairo-Bishop criteria described in Appendix 10 of the protocol) will be tabulated by dose cohort, tumor type, and in total.

Listings will be provided for DLTs, SAEs, grade 3/4/5 AEs, AEs leading to dose reduction, AEs leading to dose interruption, AEs leading to discontinuation, and AEs leading to death. Additional listings may be provided for selected AEs of special interest. Moreover, a by-subject AE data listing including, but not limited to, verbatim, PT, SOC, CTCAE grade, action taken with voruciclib, and relationship to voruciclib will be provided.

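### Combination cohorts: no TLS panel is timed to voruciclib, and the SAP's laboratory/clinical TLS table largely stops classifying events after Cycle 1 Day 8

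*Protocol*

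**What the plan says.** **Risk.** Protocol Section 4.9 states that "TLS is a known risk in subjects treated with CDK9 inhibitors" and requires risk assessment, prophylaxis and monitoring for all subjects.

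**Timed panels.** For AML, Appendix 9 asks for TLS chemistry before dosing, 6 to 8 hours after each new venetoclax dose in the ramp-up (100 mg on Day 1, 200 mg on Day 2), and finally "24 hours after reaching final ramp-up dose (i.e., pre-dose on Day 3 in Cohorts 12–25". Appendix 3, footnote c, says that the Day 22 step from 200 to 400 mg is not ramp-up, so it triggers no timed panel.

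**Voruciclib start.** Section 4.3.2.1 says for the two-weeks-on schedule: "Voruciclib dosing will be administered on Days 3–14 at the appropriate Cohort Dose". The three-weeks-on schedule runs Days 3 to 21. Voruciclib is taken at least 2 hours after venetoclax.

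**Schedules.** In Appendix 3 (combination) the row "TLS risk assessment and monitoring" is marked at Screening and Days 1, 2 and 3. Serum chemistry is marked on Days 1, 2, 3, 8 and 14 of Cycle 1 and then at Cycle 2 Day 1 (C2D1). Footnote o shows that this routine panel holds all five TLS analytes: potassium, uric acid, phosphorus, calcium and creatinine. In Appendix 2 (AML monotherapy) both rows are marked on Days 1 and 2, and voruciclib starts on Day 1.

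**Classification.** SAP Section 8.7.2 names TLS as an adverse event of special interest, the only one it names. It tabulates laboratory and clinical TLS as "determined by Modified Cairo-Bishop criteria described in Appendix 10 of the protocol". Appendix 10 says that two or more metabolic abnormalities "must be present during the same 24-hour period within 3 days before the start of therapy, or up to 7 days after". Clinical TLS requires laboratory TLS plus a clinical finding. Footnote b of Table 25 equates acute kidney injury with clinical TLS and gives no time limit.

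**The concern.** The protocol names TLS as a risk of voruciclib's own class, yet the timed monitoring ends just before voruciclib is added to venetoclax. The first days of the combination are when a rapid rise in potassium, phosphorus or uric acid would be looked for. No chemistry is scheduled in those days, although AML monotherapy has it after one day.

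The table is a separate matter. A reader of the clinical study report would take the laboratory/clinical TLS table as the summary for the whole treatment period. As defined, it covers roughly the first week and does not say so. Later TLS would have to be pieced together from adverse event terms and single-analyte laboratory grades.

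**Working it through.** No sample-size or error-rate formula applies; the check is calendar arithmetic on nominal study days.

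**1. Reproduce the plan's last timed panel.** The final ramp-up dose is on Day 2 (Appendix 3, footnote c). Day 2 + 24 hours = Day 3 before dosing, as Appendix 9 states. Voruciclib follows venetoclax by at least 2 hours on Day 3, so the number of timed panels after any voruciclib dose is 0.

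**2. Gap to the next scheduled chemistry.**
- Combination: Day 8 − Day 3 = 5 days.
- AML monotherapy: Day 2 − Day 1 = 1 day.

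Both schedules allow ±3 days per Cycle 1 visit, so nominal days are compared. The Day 8 attendance is also held in place by the pharmacokinetic sample set at "approximately 24 hours after Day 7 dose" (Section 9.14.2).

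**3. Voruciclib doses taken before that chemistry.**
- Two weeks on: Days 3–7 = 5 of 12 Cycle 1 doses (Days 3–14).
- Three weeks on: Days 3–7 = 5 of 19 (Days 3–21).
- Cohort 12, every other day: Days 3, 5, 7 = 3 of 6.

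**4. When therapy starts.** Appendix 10 does not say which drug counts. Protocol Section 8.6 starts the treatment phase on the day either drug is first given. SAP Section 7.1 counts study days from the first dose of study drug. The Synopsis starts the DLT period, and Section 6.1 starts adverse events, at venetoclax. Together these set the anchor at venetoclax on Day 1.

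**5. Window end.** Day 1 + 7 = Day 8.

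| Quantity | Outside the window |
|---|---|
| Cycle 1 days | Days 9–28 = 20 of 28 |
| Voruciclib days, two weeks on | Days 9–14 = 6 of 12 |
| Voruciclib days, three weeks on | Days 9–21 = 13 of 19 |
| Voruciclib days, Cohort 12 | Days 9, 11, 13 = 3 of 6 |
| Venetoclax 400 mg days in Cycle 1 | Days 22–28 = 7 of 7 |
| Scheduled chemistry after first voruciclib, through C2D1 (Days 8, 14, 29) | 2 of 3 |

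The one panel inside the window falls on its last day.

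**6. Sensitivity to the anchor.** If the first voruciclib dose were used instead, the window would end on Day 3 + 7 = Day 10. That leaves 18 of 28 Cycle 1 days outside, with 4 of 12, 11 of 19 and 2 of 6 voruciclib days. The 400 mg days (7 of 7) and scheduled panels (2 of 3) do not change.

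**The case against.** The case against is substantial, and much of it stands.

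- **Week-one chemistry is not sparser overall.** The combination has chemistry on Days 1, 2, 3 and 8 plus the 6-to-8-hour panels, with a longest gap of 5 days. AML monotherapy has Days 1, 2 and 8, with a gap of 6 days. A reader might infer that the combination is monitored less; the schedules do not show that. The narrower point survives: monotherapy has a sample about a day after voruciclib begins, and the combination does not.
- **TLS chemistry is not absent after voruciclib.** Routine chemistry on Days 8, 14 and C2D1 holds every analyte. Section 4.9 requires monitoring for all subjects, Section 9.7 allows extra chemistry as clinically indicated, and Appendix 9 advises more testing where risk factors exist. None of this sets a time in Days 4 to 7.
- **Late events are not lost.** They appear as adverse events and serious adverse events (SAP 8.7.2) and in the laboratory tables and listings (SAP 8.7.3). Only the laboratory/clinical label is missing, and that follows from a published definition.
- **The table is not wholly barred from late events.** The kidney-injury footnote, read alone, would admit them. Appendix 10's text requires laboratory TLS first, so the footnote is an ambiguity and does not clearly reopen the window.
- **The anchor is effectively settled.** A reader might treat Day 8 or Day 10 as an open choice, but the passages in step 4 of the working favor Day 8. Writing it down adds clarity and corrects no error.
- **Dose decisions are not distorted.** Grade 3 or higher TLS is a DLT in Cycle 1 with no 7-day limit (Section 4.4). The documents do not support an inference that escalation rules are compromised.
- **The signal so far is low.** The severe TLS cited in Appendix 9 was with other CDK inhibitors in CLL, and no combination DLT was reported from 50 mg every other day to 250 mg daily on two weeks on. That record does not cover the 300 mg level, still enrolling, or the newly added three-weeks-on schedule.

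**Conclusion.** The point holds in two limited parts. First, no TLS panel in the combination cohorts is timed to voruciclib. Nominally 5 days and 5 once-daily doses (3 in Cohort 12) pass before the next scheduled chemistry, against about 1 day in AML monotherapy. Second, the SAP's laboratory/clinical TLS table closes on Day 8. It leaves 20 of 28 Cycle 1 days, the Day 14 and C2D1 panels, the 400 mg days and all later cycles without a laboratory TLS label. They also have no clinical TLS label, except possibly through the kidney-injury footnote.

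This rests on nominal visit days, on venetoclax as the start of therapy, and on Appendix 10 being applied as written. DLT classification rules, escalation rules and the primary endpoint do not change. It is a cheap improvement of low priority.

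**What to change.** **Protocol Appendices 3 and 9, for combination subjects still to be enrolled.** Add the five-analyte TLS panel to the 6-hour pharmacokinetic draw that already follows the first voruciclib dose on Cycle 1 Day 3 (Section 9.14.2, Tables 14 and 15). Add it to the Day 4 draw when that visit takes place; the tables note "Day 4 sample to be collected only if the subject is able to visit the clinic", so no new attendance is created.

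**SAP Section 8.7.2.** Keep the published Appendix 10 definition for the main rows. Add one row for subjects who meet the Table 25 laboratory or clinical criteria outside the window at any time on treatment, labelled as outside the published definition. It uses data already collected.

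**Cost and limits.** The cost is one extra tube (two if Day 4 is attended) and amendment wording, which needs regulatory and ethical review under Protocol Section 13. More laboratory TLS may be reported. If Day 4 is skipped, 5 days − 6 hours = 4.75 days remain without scheduled chemistry, so Days 4 to 7 are only partly covered. The change adds no sample after the Day 22 step; the new SAP row would pick up only what existing panels show.
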